# 9.4 **Neo-Adjuvant Therapy Tumor Response**

Clincal (radiographic or physical exam) Response to neo-adjuvant therapy will be assessed by RECIST 1.1. The following definitions and criteria should be used for the baseline evaluations of existing disease, and for the ongoing evaluation of tumor responses prior to surgery.

**Measurable lesions** - lesions that can be accurately measured in at least one dimension with longest diameter (LD)  $\geq 10$  mm using CT, MRI, or caliper or ruler measurements or  $\geq 20$  mm with x-ray. A lymph node must be  $\geq 15$  mm in short axis when assessed by CT scan

**Non-measurable lesions** - all other lesions including small lesions (LD < 10 mm with CT, MRI, or caliper measurements or <20 mm with x-ray).

# Documentation of "Target" and "Non-Target" Lesions

- All measurable lesions up to a maximum of two lesions per organ and five lesions in total, representative of all involved organs should be identified as *target lesions* and recorded and measured at baseline.
- Target lesions should be selected on the basis of their size (lesions with the longest diameter) and their suitability for accurate repeated measurements (either by imaging techniques or clinical assessments).
- A sum of the LD for *all target lesions* will be calculated and reported as the baseline sum LD. The baseline sum LD will be used as the reference by which to characterize the objective tumor response.
- All other lesions (or sites of disease) should be identified as *non-target lesions* and should also be recorded at baseline. Measurements of these lesions are not required, but the presence or absence of each should be noted throughout follow-up.

	Evaluation of target lesions
Complete Response (CR)	Disappearance of all target lesions (Must persist for a minimum of four weeks)
Partial Response (PR)	At least a 30% decrease in the sum of the LD of target lesions, taking as reference the baseline sum LD (Must persist for a minimum of four weeks)
Progressive Disease (PD)	At least a 20% increase in the sum of the LD of target lesions, taking as reference the smallest sum LD recorded since the treatment started or the appearance of one or more new lesions

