6. Biopsies are mandatory at day 0 and surgery. Biopsies are optional at day 42 and progression. See section 13.1 for details about the collection.

7. Adverse events will be followed until resolution while the patient remains on treatment. Events will be followed for 90 post treatment for SAEs and events thought to be related to the study medication will be followed until resolution or stabilization of the adverse event, or until the patient starts a new treatment regimen.

8. Surgery should occur no later than 28 days after D84.

9. Adjuvant nivolumab should be initiated within 90 days after definitive surgery.

10. EOT visit should occur 28 days (+-14 days) after the completion of therapy.

11. Follow-up should occur every three months (+-or 14 days) for 1 years post EOT visit.

12. Surgery will reset the scan schedule and should occur approximately every 12 weeks after surgery as standard of care.

13. Pathology at surgery will be used to determine pathological response.

14. Collection of blood samples for correlatives is optional and will be collected prior to HF10 injection during the neo-adjuvant (days 0,7, 14, 21, 28, 42, 56, 70, 84) and prior to nivolumab infusion during the adjuvant nivolumab administration.

15. Men and women of childbearing potential must agree to use adequate contraception from the time of consent through 7 months after nivolumab study treatment (neoadjuvant and adjuvant). A pregnancy test will be conducted w/in 72 hours prior to beginning adjuvant nivolumab.

16. Next generation sequeencing is required at screening as per standard of care. Testing will include, but is not limited to BRAF mutational analysis.

17. Thyroid Tests will include TSH and free T4. In the event of hypo/hyper thyroidism, appropriate support will be provided in accordance with institutional guidelines.

18. Lesion photography should be completed at each time point AND when a new lesion is identified.

19. irRC and RECIST should be done prior to surgery. Only RECIST will be used as clinical response criteria and used to make treatment decisions

Protocol name: Phase II Neoadjuvant trial of Nivolumab in Combination with HF10 Oncolytic Viral Therapy in Resectable Stage IIIB, IIIc, IVM1a Melanoma (Neo-NivoHF10) Version Date: 22JUL2019 Principal Investigator: [name]

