# 9.5 irRC and RECIST 1.1 Concordance

Exploratory objectives for this study include review of the concordance between irRC and RECIST 1.1 response assessments. Both irRC and RECIST 1.1 response assessments will be performed at all timepoints prior to surgery.

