# Immune-Related Response Criteria (irRC)

Clinical response assessments will be performed according to irRC (Wolchok, 2009)

Table 1: Overall Response using irRC:

Response Assessment	Description	
irCR	Complete disappearance of all lesions (whether measurable or not, and no new lesions)	
	Confirmation by repeat, consecutive assessment $\geq$ 4 weeks after first documentation.	
irPR	Decrease in tumor burden ≥50% relative to baseline	
	Confirmed by a consecutive assessment $\geq$ 4 weeks after first documentation.	
irSD	Not meeting criteria for irCR or irPR, in absence of irPD. A change in tumor burden of neither 50% decrease from baseline nor 25% increase from nadir can be determined.	
irPD	Increase in tumor burden ≥25% relative to nadir (minimum recorded tumor burden)	
	Confirmation by a repeat, consecutive assessment $\geq 4$ weeks after the first documentation.	

Abbreviations: CR= Complete Response; irRC= Immune-Related Response Criteria; PD= Progressive Disease; PR=Partial Response; SD=Stable Disease

Measurable Response	Non-measurable response		
Target and new, measurable lesions % change in tumor burden	Non-target lesions	New non- measurable lesions	Overall irRC Response
$\downarrow 100^{1}$	Absent	Absent	irCR 
↓ 100 	Stable	Any	irPR 
↓ 100 	Unequivocal progression	Any	irPR 
$\downarrow \ge 50^1$	Absent or Stable	Any	irPR 
$\downarrow \ge 50^1$	Unequivocal progression	Any	irPR 

Table 2: Derivation of irRC overall responses

Protocol name: Phase II Neoadjuvant trial of Nivolumab in Combination with HF10 Oncolytic Viral Therapy in Resectable Stage IIIB, IIIc, IVM1a Melanoma (Neo-NivoHF10) Version Date: 22JUL2019 Principal Investigator: [name]

$\downarrow \ge 50 \text{ to } \uparrow < 25^1$	Absent or Stable	Any	irSD
$\downarrow \ge 50$ to $\uparrow < 25^1$	Unequivocal Progression	Any	irSD
$\uparrow \ge 25^2$	Any	Any	irPD 

Decrease relative to baseline

 Increase relative to nadir

 confirmed by consecutive scan  $\geq$ 4 weeks after first documentation

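### Pre-surgical response must last or be confirmed over four weeks, but only one post-baseline assessment (D84) is scheduled before surgery, so the schedule cannot establish a confirmed CR, PR or irPD

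*Combined protocol and SAP*

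**What the plan says.** **Response definitions.** In Section 9.4 the RECIST 1.1 table defines CR as "Disappearance of all target lesions (Must persist for a minimum of four weeks". PR is a decrease of at least 30% in the sum of longest diameters, "taking as reference the baseline sum LD (Must persist for a minimum of four weeks". RECIST PD carries no such condition. In Section 9.5, irRC Table 1 attaches "Confirmation by repeat, consecutive assessment" to irCR and "Confirmed by a consecutive assessment" to irPR, each at 4 weeks or more after first documentation, and sets the same requirement for irPD. A footnote to irRC Table 2 repeats it.

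**Schedule.** In the Section 8 calendar, the RECIST 1.1 and irRC rows are marked at two points only: pre-study and D84±4. Radiologic evaluation before surgery is scheduled at the same two points. It is also marked at the end-of-treatment or progression visit, but no RECIST or irRC reading is marked there. Footnote 19 says "irRC and RECIST should be done prior to surgery" and names no repeat. Footnote 8 says "Surgery should occur no later than 28 days after D84", Section 6.1.2 gives the same 28-day limit from the end of neoadjuvant therapy, and footnote 12 restarts the scan schedule after surgery.

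**Wording that suggests more assessments.** Section 9.4 describes its criteria as serving a continuing evaluation of response before surgery. Section 9.5 says "Both irRC and RECIST 1.1 response assessments will be performed at all timepoints prior to surgery".

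**Endpoints that depend on this.** Secondary objective 1.2.3 (tumor response before surgery by RECIST 1.1, radiographic or clinical) and exploratory objective 1.3.2 (concordance of irRC with RECIST 1.1). Section 10 gives no analysis rule for pre-surgical response.

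**The concern.** Both sets of criteria need a second look at least four weeks after the first. The calendar provides one look after baseline, and the lesions are then resected. The protocol therefore defines a category of response that its own schedule does not collect the data to assign.

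The analyst would have to choose between ignoring the four-week conditions and counting every D84 responder as a non-responder. Nothing in Section 10 settles that choice, so it could be made after the data are seen. The two options can give very different response rates.

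Concordance is affected in a different way. For CR and PR, neither criterion yields a confirmed responder from the scheduled data. For progression, the confirmation rule applies to irPD but not to RECIST PD, so the rules themselves can separate the two criteria.

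**Working it through.** **The plan's own figure.** The only computed design figures are the power values in Section 10. With n = 20, a 5% null rate and rejection at 4 or more responses, P(X ≥ 4 | 20, 0.20) = 0.589 and P(X ≥ 4 | 20, 0.30) = 0.893, with exact one-sided alpha 0.0159. The stated 59% and 89% reproduce. They concern the pathologic endpoint, and this point does not depend on them.

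**Step 1: assessments needed and available.** A four-week persistence or confirmation rule needs two post-baseline assessments at least 28 days apart. The calendar supplies one (D84±4).

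**Step 2: room for a repeat before surgery.** Slack = (latest surgery day − assessment day) − 28.

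| Assessment day | Latest surgery day | Gap (days) | Slack (days) |
|---|---|---|---|
| D84 | D112 (84 + 28) | 28 | 0 |
| D80 | D112, deadline counted from nominal D84 | 32 | +4 |
| D88 | D112, deadline counted from nominal D84 | 24 | −4 |

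The calendar states its windows in business days. If 4 business days span up to 6 calendar days (my assumption), the range is D78 (gap 34, slack +6) to D90 (gap 22, slack −6). If the deadline runs from the actual D84 visit, slack is 0. With the assessment on D84, any surgery 1 to 27 days later leaves no room for a four-week repeat. Where room exists, the repeat is still not scheduled.

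**Step 3: could D84 itself be the confirming assessment?** The response would have to be first documented by day 84 − 28 = 56 (day 52 for an assessment on D80, day 60 for D88). Physical examination is scheduled at D56, but no RECIST, irRC or radiologic evaluation is.

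**Step 4: the literal result.** If an unconfirmed response does not count, the planned 20 patients give 0 responders. The exact upper 95% limit for 0/20 is 1 − 0.025^(1/20) = 0.168, so the interval is 0 to 16.8%. The result does not depend on the treatment effect.

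**Step 5: concordance.**
- A D84 increase large enough to meet both thresholds (20% for RECIST, 25% for irRC) is RECIST PD at once but remains an unconfirmed irPD.
- A new measurable lesion is RECIST PD under Section 9.4. In irRC Table 2, target and new measurable lesions are assessed together as tumor burden.

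Disagreement is therefore possible, and part of it comes from the confirmation rule alone.

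**Secondary check: irRC Table 2.** The irPR rows cover a decrease of 50% or more. Both irSD rows, as they read in the available text, run from a decrease of 50% or more to an increase below 25%. A 60% decrease with stable non-target lesions fits both. Table 1 describes irSD as "A change in tumor burden of neither 50% decrease from baseline nor 25% increase from nadir can be determined" and limits it to cases that do not meet irCR or irPR, so under Table 1 that patient is irPR.

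**The case against.** The strongest reply is that a response can persist without a second scan. Section 9.4 accepts physical examination and caliper or ruler measurement, and objective 1.2.3 allows clinical assessment. Eligible injectable lesions are cutaneous, subcutaneous or nodal. Physical examination is scheduled at every neoadjuvant visit, lesion photography is marked at D14, D28, D42 and D84, and HF10 volume depends on lesion size. D56 to D84 is exactly 28 days. For superficial disease an investigator could therefore document persistence within existing visits. This stands as a limit on the point: the gap is clearest for irRC and for lesions measured only by imaging. It does not close the gap, because no RECIST or irRC assessment is scheduled at those earlier visits.

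The reply also rules out four stronger readings that a reader might infer:

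- *Confirmation is impossible.* The documents do not support this. A repeat on the last permitted day, or after an early-window D84 assessment, could reach four weeks. It is unscheduled, not impossible.
- *Objective 1.2.3 cannot be answered at all.* RECIST SD and PD need no confirmation and can be assigned at D84. Only CR and PR are impaired.
- *Concordance is agreement by construction.* That could be said only of CR and PR, where neither criterion confirms anyone from the scheduled data. Progression can be discordant, as step 5 shows.
- *Table 2 puts a patient in two classes.* Table 1 resolves the class, and the symbol may have been misread when the table was converted to text.

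The appeal to "Both irRC and RECIST 1.1 response assessments will be performed at all timepoints prior to surgery" does not help the plan. The calendar has one post-baseline timepoint for these criteria. If more were intended, the text and the calendar disagree and still have to be reconciled.

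**Conclusion.** The plan is wrong as written on this point and should be fixed. The scheduled assessments cannot establish a confirmed pre-surgical CR or PR under RECIST 1.1 or irRC, or a confirmed irPD. Concordance would be distorted by the unequal confirmation rules for progression.

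The size depends on how the rule is applied. Taken literally it yields 0/20 (exact 95% CI 0 to 16.8%), which illustrates the rule and does not predict what would be reported. This rests on three assumptions: the calendar defines when RECIST and irRC are done, no unscheduled repeat is made, and an unconfirmed response counts as a non-response.

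It falls short of a must-fix. The primary pathologic endpoint, its test and its power are untouched, Section 10 attaches no test to RECIST response, and concordance is exploratory and descriptive. The irSD rows of Table 2 are a minor secondary matter.

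**What to change.** 1. For objectives 1.2.3 and 1.3.2, define the endpoint as unconfirmed response at the D84 pre-surgical assessment.
2. In Section 9.4, delete the four-week persistence condition from CR and PR.
3. In Section 9.5, state that irRC confirmation does not apply to this assessment.
4. Label the response rates and the concordance as unconfirmed wherever they are reported.
5. Align the Section 9.4 wording on continuing evaluation and the Section 9.5 wording on assessment timepoints with the calendar.
6. Check the two irSD rows of irRC Table 2 against the source file. If they read as shown, change them to a decrease of less than 50% up to an increase of less than 25%, to match Table 1.

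The cost is wording only, with no extra scans or visits. The drawback is that the response rates are unconfirmed. Prespecifying clinical measurement at existing visits could keep a persistence requirement for superficial lesions, but it would not cover lesions measured only by imaging. The timing of surgery is a clinical matter on which no view is taken here.

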5.1 Inclusion Criteria

# Yes/No (Response of "no" = patient ineligible)

- **5.1.1** Patients must be  $\geq 18$  years or older.
- **5.1.2** Patients must have stage IIIB, IIIC, or IVM1a (equivalent staging at time of enrollment via AJCC 7th edition) metastatic melanoma which is eligible for complete surgical resection.
- **5.1.3** Prior systemic, regional and radiation anticancer therapies must have been completed at least three months prior to enrollment. Prior therapies (including anti-PD-1 inhibitors) are allowed provided three months have elapsed from last dose.
- **5.1.4** Patients must be a candidate for intralesional therapy.
  - At least 1 injectable cutaneous, subcutaneous, or nodal melanoma lesion  $\geq 10$  mm in longest diameter

OR

• Multiple injectable melanoma lesions which in aggregate have a longest diameter of  $\geq 10$  mm

AND

- Must have no known bleeding diathesis or coagulopathy that would make intratumoral injection unsafe.
- **5.1.5** Patients must have an Eastern Cooperative Oncology Group (ECOG) performance status of 0 or 1.
- **5.1.6** Serum LDH level  $\leq$  1.5 upper limit of normal (ULN) within 28 days prior to enrollment.
- **5.1.7** Patients have adequate organ function within 28 days prior to enrollment, as defined in table 1 listed below.

Table 1: Adequate Organ Function Laboratory Values:

Protocol name: Phase II Neoadjuvant trial of Nivolumab in Combination with HF10 Oncolytic Viral Therapy in Resectable Stage IIIB, IIIc, IVM1a Melanoma (Neo-NivoHF10) Version Date: 22JUL2019 Principal Investigator: [name]

System	Laboratory Value
Hematological:	
Absolute Neutrophil Count ANC	≥ 1,500/uL
Platelets	≥ 100,000/uL
Hemoglobin	$\geq$ 9 g/dL
Renal	
Serum Creatinine OR measured calculated creatinine clearance (GFR may also be used in place of creatinine or CrCl)	$\leq$ 1.5 upper limit of normal (ULN) OR $\geq$ 60 mL/min for subject with creatinine levels $\geq$ 1.5 X institutional ULN
Hepatic	
Serum total bilirubin	$\leq$ 1.5 X ULN OR Direct bilirubin $\leq$ ULN for subjects with total bilirubin $\geq$ 1.5 ULN
AST or ALT	
 
≤ 2.5 X ULN OR
 
≤ 5 X ULN for subjects with liver metastases
 

- **5.1.8** Men and women of childbearing potential must agree to use adequate contraception from the time of consent through 7 months after final nivolumab study treatment.

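### The printed RECIST progression rule has no minimum absolute increase and no confirmation, so when one small lesion is the whole target sum, measurement error can be recorded as progression

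*Combined protocol and SAP*

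**What the plan says.** Section 9.4 states that "Response to neo-adjuvant therapy will be assessed by RECIST 1.1" and then that "The following definitions and criteria should be used for the baseline evaluations of existing disease" and for later tumor responses before surgery. A site therefore works from the printed table.

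In that table, PD for target lesions is "At least a 20% increase in the sum of the LD of target lesions". The increase is counted from the lowest sum seen on treatment, and a new lesion also qualifies. No absolute increase is required there or anywhere else in the document. Complete and partial response must persist for four weeks; the PD row has no such condition. By contrast, Section 9.5 sets irPD at a 25% increase over nadir, confirmed at least 4 weeks later.

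Three other provisions decide how small the sum can be:

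- Section 9.4 makes a lesion measurable from 10 mm longest diameter by CT, MRI, caliper or ruler; a node assessed by CT must be at least 15 mm in short axis.
- Section 5.1.4 accepts "At least 1 injectable cutaneous, subcutaneous, or nodal melanoma lesion" of at least 10 mm as sufficient for entry.
- Section 9.4 selects as targets "All measurable lesions up to a maximum of two lesions per organ and five lesions in total".

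The Section 8 calendar schedules RECIST pre-study and at D84 only. Footnote 19 adds: "Only RECIST will be used as clinical response criteria and used to make treatment decisions".

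**The concern.** A purely relative threshold shrinks with the lesion. Eligibility requires skin, subcutaneous or nodal disease suitable for injection and excludes active visceral, central nervous system and bone metastases, so small target sums are allowed. At a 10 mm sum the PD line is 12 mm, and at 15 mm it is 18 mm. Differences of that size can arise from measurement alone, and with one scheduled follow-up assessment and no confirmation, one reading settles the call.

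At stake is whether unchanged disease is recorded as stable disease (SD) or PD in the pre-surgical response (objective 1.2.3). The irRC/RECIST concordance (objective 1.3.2) is affected too. A spurious 20% rise in a small lesion is PD under the printed RECIST table, but irRC asks for a larger rise and a repeat assessment. Some discordance would then come from how the two tables are written, not from how the tumors behave.

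**Working it through.** The plan prints no figure for this rule, so there is none to reproduce.

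**Growth needed for PD** = 0.20 × reference sum. With only two scheduled assessments, the reference is usually the baseline sum.

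| Reference sum | 20% rule | With an illustrative 5 mm minimum |
|---|---|---|
| 10 mm | 2 mm | 5 mm |
| 15 mm | 3 mm | 5 mm |
| 20 mm | 4 mm | 5 mm |
| 25 mm | 5 mm | 5 mm (no change) |
| 30 mm | 6 mm | 6 mm (no change) |

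A 5 mm minimum binds only when 0.20 × sum < 5, that is, below 25 mm.

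**The rule acts on the sum.** If one lesion grows from 10 to 12 mm, the sum rises 20% with one target, 10% with two 10 mm targets, 6.7% with three and 4% with five. Only the first is PD.

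**Chance of a false PD for an unchanged single lesion.** Let the true size be L, and let the baseline reading B and follow-up reading F be independent Normal(L, s). The documents do not give s; I assume 1.0 to 1.5 mm as the main range.

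Step 1, ignoring the measurability limit. PD is F ≥ 1.2B, and F − 1.2B has mean −0.2L and standard deviation s√(1 + 1.44) = s√2.44 = 1.562s. So P = 1 − Φ(0.2L / 1.562s).

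- L = 15: 3/1.562 = 1.92, giving 2.7% (s = 1.0); 3/2.343 = 1.28, giving 10.0% (s = 1.5).
- L = 20: 4/1.562 = 2.56, giving 0.5%; 4/2.343 = 1.71, giving 4.4%.

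Step 2, applying the limit. A lesion read below 10 mm at baseline is not measurable and cannot be a target. The relevant quantity is P(F ≥ 1.2B given B ≥ 10), which is the integral over b ≥ 10 of the density of B times 1 − Φ((1.2b − L)/s), divided by 1 − Φ((10 − L)/s).

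| True size | Step 1, s = 1.0 / 1.5 | Step 2, s = 1.0 / 1.5 |
|---|---|---|
| 10 mm | 10.0% / 19.7% | 0.5% / 2.6% |
| 12 mm | 6.2% / 15.3% | 4.8% / 9.9% |
| 15 mm | 2.7% / 10.0% | 2.7% / 10.0% |
| 20 mm | 0.5% / 4.4% | 0.5% / 4.4% |

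The limit matters most at 10 mm, because a lesion that qualifies has already been read at or above its true size. By 15 mm it makes almost no difference.

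**With an illustrative 5 mm minimum.** For reference sums below 25 mm, PD then needs F − B ≥ 5, with chance 1 − Φ(5 / (s√2)) before the limit is applied: 5/1.414 = 3.54, giving 0.02% (s = 1.0); 5/2.121 = 2.36, giving 0.9% (s = 1.5). The limit only lowers these.

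**Sensitivity to s.** At s = 0.5 mm the step 1 formula gives about 0.1% at 12 mm (2.4/0.781 = 3.07) and less at 15 and 20 mm; at 10 mm it gives 0.5%, which falls to about 0% under step 2. At s = 2 mm step 1 gives 17% at 15 mm and 10% at 20 mm, and the 5 mm minimum leaves about 3.9% (5/2.828 = 1.77).

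**The case against.** The strongest reply has four parts.

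**Inputs.** Neither reading error nor the distribution of lesion sizes is documented. The plan picks the longest lesions, sums up to five, and its HF10 volume table runs to lesions over 5 cm, so many patients may have sums at which a 5 mm minimum would change nothing. This stands. The percentages are conditional on an assumed error and a single-lesion sum, and they say nothing about how many of the 20 patients would be affected.

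**The 10 mm case.** A reader might infer that a 10 mm lesion is the worst case, with a false-PD chance of 10% to 20%. That ignores the measurability limit; with it, the chance is 0.5% to 2.6%. The exposure lies more at 12 to 15 mm, where it remains.

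**The 5 mm value.** It appears nowhere in the documents as a progression minimum. This stands, and I use it only as an illustration. The gap itself does not depend on it: a criterion is named, a table is printed for use, and that table has neither a minimum nor a confirmation step.

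**Reach.** A reader might infer from footnote 19 that a false PD keeps a patient from surgery and so out of the primary analysis. The documents do not show this. Section 6.5 does not list progression among the withdrawal reasons, Section 6.1.2 turns on patients who cannot proceed to surgery, and no passage says that RECIST PD cancels it. The primary endpoint is pathologic response, so its definition and stated power do not use this rule. Section 9.3 bases progression for recurrence-free survival on irRC. The CR and PR criteria are also unchanged.

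**Conclusion.** The point holds in a limited form. As printed, the PD row lets 2 to 3 mm of apparent growth count as progression when a single lesion of 10 to 15 mm is the whole target sum, on one unconfirmed reading. Under independent Normal errors with a standard deviation of 1.0 to 1.5 mm, and a baseline reading of at least 10 mm, the false-PD chance for unchanged disease peaks at about 10% for lesions of 12 to 15 mm. It is lower at 10 and 20 mm, and negligible if the error is nearer 0.5 mm.

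It would be too strong to say that measurement error is routinely read as PD, or that any 10 mm target growing 2 mm progresses; with two or more such targets it does not. What is affected is the SD/PD split in a secondary objective and an exploratory, descriptive concordance.

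**What to change.** In the Section 9.4 target-lesion table, define PD as a 20% increase in the sum **and** a minimum absolute increase in that sum, or the appearance of new lesions. Take the minimum from the RECIST 1.1 criterion that the section names; the 5 mm used here is an assumption to be checked against that source. The SD row needs no edit, because it is defined as neither PR nor PD.

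Separately, reconcile the printed row with footnote 19 of the Section 8 calendar, which relies on RECIST for treatment decisions, so that both refer to the same definition. How a PD call should bear on treatment is a clinical matter outside this point.

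The cost is one line of text, with no new visits or data. The downside is that true growth below the minimum in very small lesions would be recorded as SD at D84.
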